6. RADIATION THERAPY

6.1 Radiation therapy schedule

Radiation therapy will be delivered to all intended fields, once daily, excluding holidays, weekends, and unavoidable factors limiting machine or patient availability.

Conventional fractionation: 25 fractions of radiation therapy (daily, Monday through Friday) to the chest wall with or without internal mammary nodes, and 23-25 fractions to the supraclavicular (with or without axillary) lymph nodes. Each fraction will consist of 200 cGy per day. Total dose = 5000 cGy to the chest wall and 4600-5000 cGy to the lymph nodes.

Hypofractionation: 16 fractions of radiation therapy (daily, Monday through Friday) to the chest wall with or without internal mammary nodes, and 15 fractions to the supraclavicular (with or without axillary) lymph nodes. Each fraction consists of 266 cGy per day. Total dose = 4256 cGy to the chest wall and 3990 cGy to the lymph nodes.

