6.8 Radiation adverse events and reporting

All participants will be seen weekly, according to their treatment plan, by an attending radiation oncologist while undergoing treatment. Side effects will be recorded and managed using clinical discretion. For information about adverse events, see Adverse Event Reporting section of protocol. Details on the adverse event reporting can be found in the AE section of the protocol.

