7. ADVERSE EVENTS REPORTING REQUIREMENTS

Adverse event (AE) monitoring and reporting is a routine part of every clinical trial.

Summary of how to collect and report adverse events (AEs) for the FABREC trial:

1. **Standard Care** All patients will be seen per their treatment plan by an attending radiation oncologist while undergoing treatment. **All adverse events** should be recorded in the patient's medical record per standard practice at your site and managed using clinical discretion. On the Medical Record Review CRFs for the FABREC Study, Clinical Research Professionals (CRPs) will be asked to report AEs as documented in the patients' charts; these medical record reviews will be done at pre-specified timepoints.
2. **Routine Solicited Adverse Events** will not be collected for the FABREC Trial.
3. **Reportable Serious Adverse Events** should be reported using the FABREC Serious Adverse Event CRF each time a reportable SAE occurs. These CRFs should be submitted using InForm. For a list of reportable SAEs, see below.

7.1 **Routine Adverse Events**

Routine Adverse Events will not be collected for the FABREC Trial. **Only events outlined in Section 7.2 should be reported via InForm.**

7.2 **Reportable Serious Adverse Events**

Reportable Serious Adverse Events that occur at any time between initiation of PMRT and 3-years after the initiation of PMRT must be reported using the FABREC Serious Adverse Event CRF. In general, the CRF should be submitted via InForm within 5 calendar days of the AE date. When an adverse event occurs at an institution outside the enrolling site, there may be a delay between when an adverse event occurs and when the study team is alerted to the event. In these instances, it is acceptable for the study team to submit those adverse events in InForm within 5 calendar days of being notified about the event and will not incur a violation.

Only "reportable SAEs" require reporting. For the FABREC trial, a reportable SAE is defined as:

- Grade 1, 2, or 3 **brachial plexopathy** (per NCI CTCAE v 4.03, this AE does not have grade 4 or 5)
- Grade 3 **chest wall pain** (per NCI CTCAE v 4.03, this AE does not have grade 4 or 5)
- Grade 3 **lymphedema** (per NCI CTCAE v 4.03, this AE does not have grade 4 or 5)
- Grade 3, 4, or 5 **myocardial infarction**
- Grade 1, 2, 3, 4, or 5 **pneumonitis**

- Grade 3, 4, or 5 **treatment related secondary malignancy**
- Grade 3, 4, or 5 **wound infection**

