After "Annual Follow up 10 of 10"	➤ Off-study CRF	Site CRP or CSC should: ➤ Submit electronically via InForm
As needed, at any time from baseline through end of 10-year follow up period	➤ Change in Status CRF	Site CRP or CSC should: ➤ Submit electronically via InForm

[^]The "12-months" timepoint (defined as 12-months after initiation of PMRT) and the "Annual Follow up 1 of 10" timepoint (defined as 1-year after initiation of PMRT) overlap, meaning that they both occur on the same date.

Note about missing forms:

- If any of the following forms are missing for a participant, then this would constitute a major protocol violation:
 - Eligibility checklist
 - Baseline Medical Record Review CRF
 - Solicited Adverse Event CRF
 - Cosmetic Outcomes CRF
 - Off Treatment CRF
 - Expedited Serious Adverse Event (SAE) Reporting CRF
 - Follow-up Medical Record Review CRF
 - Change in Status CRF

- The following questionnaires **are required**; however, if any of the following are missing for a participant despite best efforts by Central Study Coordinator and Site Staff to collect from participant, then this does not constitute a major or minor protocol violation:
 - Baseline Patient Questionnaire
 - 6-month Patient Questionnaire
 - 12-month Patient Questionnaire
 - 18-month Patient Questionnaire
 - Reconstruction photographs (at baseline, 6, 12, and 18 months)

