We will analyze adverse events toxicities experienced by all patients on the study. Adverse event rates will be summarized by types of adverse event (serious/non-serious, grade, and attribution) for each treatment arm, and they will be compared between the arms by using Fisher’s exact test. Toxicity data will be monitored by the DSMB every 6 months to assure safety of the participants (see Section 11).

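### Section 10f plans Fisher tests on non-serious adverse events that are captured only from discretionary charting, and long-course patients have more opportunity to be charted

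*Combined protocol and SAP*

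**What the plan says.** Section 10f (AE Monitoring) sets the analysis: "Adverse event rates will be summarized by types of adverse event (serious/non-serious, grade, and attribution) for each treatment arm". Long-course and short-course rates are then to be tested against each other with Fisher's exact method. The section names no time window, significance level, restriction to particular events or allowance for how events were found. Toxicity data also go to the DSMB every 6 months.

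Section 7 sets the collection. Section 7.1 states: "Routine Adverse Events will not be collected for the FABREC Trial", and limits event reporting in the database to the section 7.2 list. The summary that opens section 7 also excludes routine solicited events, but says that site research staff "will be asked to report AEs as documented in the patients' charts; these medical record reviews will be done at pre-specified timepoints". Section 8 confirms that the chart-review forms gather toxicities and that the protocol mandates no study visits.

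Section 6.8 describes what the chart will hold: "All participants will be seen weekly, according to their treatment plan, by an attending radiation oncologist while undergoing treatment". It adds: "Side effects will be recorded and managed using clinical discretion". Section 6.1 gives the course lengths. For one arm it reads "Conventional fractionation: 25 fractions of radiation therapy (daily, Monday through Friday) to the chest wall"; the other arm has 16 chest-wall fractions on the same weekday schedule.

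The section 7.2 events are reportable from the start of radiation to 3 years after it in both arms. The missing-forms note in section 9.1 still lists a "Solicited Adverse Event CRF" among the forms whose absence is a major violation.

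**The concern.** A between-arm test of event rates assumes that an event of given severity is equally likely to be recorded in either arm. For non-serious events the plan does not secure that. Recording is discretionary, it takes place largely at weekly visits during treatment, and one arm is on treatment for longer. The schedule of assessments also times the first post-treatment chart review at 30 days after radiation ends, not from its start, so that review spans a longer period on long-course.

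Both features act in the same direction: fewer chances to chart a mild toxicity on short-course. A lower recorded rate there could be read as lower toxicity. The same shortfall could make the short-course arm look quieter than it is in the six-monthly DSMB tables.

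**Working it through.** Section 10f gives no rate, power or sample size, so there is no planned figure to reproduce. The check asks how often the planned test would reject if the arms did not truly differ.

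**Inputs from the documents**
- Fractions: 25 versus 16, five per week (section 6.1).
- Visits: weekly during treatment (section 6.8).
- Sample size: 400 randomised 1:1, so 200 per arm (section 5.3).
- Test: Fisher's exact (section 10f).

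**Assumptions**
- Two-sided 0.05, borrowed from the primary analysis because 10f states no level.
- The chance that a visit leads to a chart entry, which the documents do not give.

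**Exposure**
- Long-course: 25/5 = 5.0 weeks, about 5 visits.
- Short-course: 16/5 = 3.2 weeks, 3-4 visits.
- Radiation start to the 30-day review: 5.0 × 7 + 30 = 65 days versus 3.2 × 7 + 30 = 52.4 days, a gap of about 12.6 days.

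**Model A: each visit is an independent chance q of a charted event.** The recorded rate is 1 − (1 − q)^visits. Rejection probabilities come from full enumeration of the exact test.

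| q | Recorded, 5 visits | 4 visits | 3 visits | Rejects, 5 vs 4 | Rejects, 5 vs 3 |
|---|---|---|---|---|---|
| 0.02 | 9.6% | 7.8% | 5.9% | 7% | 23% |
| 0.05 | 22.6% | 18.6% | 14.3% | 14% | 53% |
| 0.10 | 41.0% | 34.4% | 27.1% | 24% | 81% |
| 0.20 | 67.2% | 59.0% | 48.8% | 36% | 95% |
| 0.30 | 83.2% | 76.0% | 65.7% | 38% | 98% |

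Worked line at q = 0.10: 1 − 0.9^5 = 0.410, 1 − 0.9^4 = 0.344, 1 − 0.9^3 = 0.271. Nearly all rejections favour short-course. With 5 visits in both arms the test rejects in 3.3%-3.9% of trials over the same range of q, so the excess comes from unequal visits.

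**Model A plus two further contacts per arm after treatment (an assumption).** At q = 0.10 the comparison becomes 7 versus 6 or 5 opportunities: 52.2% versus 46.9% or 41.0% recorded. Rejection falls to 16% and 58%. Over q = 0.02-0.30 it is 6%-20% (5 vs 4 on treatment) and 16%-73% (5 vs 3).

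**Model B: toxicity, once present, persists through treatment.** True incidence I is equal in both arms and each visit charts it with probability r. The recorded rate is I × [1 − (1 − r)^visits], on-treatment visits only, with I from 20% to 60%.

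| r | Rejects, 5 vs 4 | Rejects, 5 vs 3 |
|---|---|---|
| 0.5-0.7 | 4%-5% | 4%-18% |
| 0.3 | 5%-12% | 13%-52% |

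Worked line at I = 60%, r = 0.5: 0.6 × (1 − 0.5^5) = 58.1% versus 0.6 × (1 − 0.5^3) = 52.5%, giving rejection in 18%. With good charting and 4 short-course visits, the test behaves almost as it would with equal visits.

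**The case against.** The strongest reply is that the size depends on the model. Independent visits make each extra visit a fresh chance of an event, whereas a toxicity missed one week can be charted the next. Model B shows that good charting of persistent toxicity leaves little or no inflation. This stands, and it is why no single figure is claimed.

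Second, 16 = 3 × 5 + 1, so the short course reaches a fourth treatment week and 4 visits are plausible. The 5-versus-3 column is then an upper case. This also stands, although the protocol does not say whether a visit falls in a final week with a single fraction.

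Third, chart review continues at 12 months and yearly in both arms. This dilutes the imbalance but does not remove it.

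Fourth, section 10f is a monitoring section without a stated hypothesis or power. Neither the primary endpoint nor the 18-month reconstruction success composite in section 10c depends on it. That limits the stakes, but 10f still commits to the test.

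A reader might also infer that the serious-event comparison is compromised because the section 7.2 list includes grade 1-2 pneumonitis and brachial plexopathy. The documents do not support that. The list and the 3-year clock are the same in both arms, and 10f also summarises by grade. The label may be unusual, but it creates no difference between arms. Some sensitivity of these low-grade events to visit frequency remains.

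**Conclusion.** The concern holds for non-serious, chart-abstracted events. The mismatch between sections 7 and 10f is on the face of the protocol, and the direction follows from the visit schedule: more opportunity to record on long-course, so a possible apparent advantage for short-course.

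The size cannot be derived from the documents. False rejection at 200 per arm runs from about 4%, which is no real inflation, to 24% or 81% at an assumed independent 10% per visit, depending on whether short-course has 4 or 3 visits. Shared later follow-up lowers the last two figures. All of this assumes that weekly visits take place as section 6.8 describes.

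Two stronger readings should be resisted. One is that the plan builds in a false difference of known size; the charting probability is nowhere given. The other is that non-serious events are not captured at all; chart review does capture some, but not systematically. The section 7.2 comparison is much less exposed. The point merits a change to a secondary analysis and does not threaten the trial's main conclusions.

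**What to change.** In section 10f:
- Restrict formal between-arm tests to the section 7.2 reportable events, counted from radiation start to 3 years in both arms and presented by grade.
- State two limits of that comparison: sections 7.2 and 8 end follow-up at distant recurrence, so not every patient is observed for 3 years; and grade 1-2 pneumonitis and plexopathy remain somewhat sensitive to how often patients are seen.
- Report chart-abstracted non-serious toxicities by arm descriptively, without p-values, noting that recording was discretionary and that opportunity to record differed by arm.

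The cost is the loss of p-values for non-serious events. No new visits, data or patients are needed.

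As a separate minor item, reconcile the Solicited Adverse Event form in section 9.1 with section 7, which says that such events are not collected. This is an inconsistency between forms and does not bear on the comparison above.

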2.2 Objectives

Objective 1: Compare the effect of short-course versus long-course post-mastectomy radiation therapy on highly-relevant patient-reported outcomes (PROs) and outcomes prioritized by individual trial participants.

Our primary outcome is the Physical Well Being (PWB) domain of the FACT-B instrument. PRO assessment will be further patient-focused, as we will also ask each subject to choose the FACT-B subdomain most relevant to their experience and separately correlate this domain to that patient's radiation schedule. We will thereby create a more

patient-centered outcome by comparing short- versus long-course radiation according to the subscale selected to be most important to the individual patient. In addition, we will assess pain, arm mobility, lymphedema, self-image, satisfaction with decision to undergo reconstruction, sexual well-being, functional well-being, and treatment burden in all patients using standard instruments.

Hypothesis: Short-course radiation therapy will improve patient quality of life in multiple domains.

Objective 2: Compare clinical outcomes for patients receiving short-course versus long-course radiation.

These include complications and clinically-assessed cosmetic results. We will also create an infrastructure to monitor long term oncologic outcomes such as recurrence and breast-cancer specific survival, and rare radiation side effects (secondary malignancy and brachial plexopathy).

Hypothesis: Short-course radiation therapy will decrease complications, improve clinician-quantified cosmetic results, and will have no increased risk of local or regional recurrence or side-effects.

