5.3 Stratification Factors and Treatment Assignment

400 patients will be randomized 1:1 into either Arm 1 (short-course PMRT) or Arm 2 (long-course PMRT).

Randomization will be stratified by treatment center and age of the patient (<45 vs. ≥45).

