The primary analysis and power: We hypothesize that hypofractionated (short-course) radiation therapy has a higher reconstruction success rate, compared to the conventional fractionation (long-course) radiation at 18-months. We will use Chi-square test for 2x2 table to test this superiority hypothesis. We will also construct a two-sided 95% confidence interval for the difference in the composite outcome of reconstruction success likelihood (defined as no major complications, presence of reconstruction, and good or excellent cosmetic outcome). Recent estimates of reconstruction success after implant reconstruction and conventional radiation reveal a 71% likelihood at the 2-year time period.⁴⁶ “**Table: Effect size and power for superiority tests**” shows the available power with various reconstruction success probabilities for hypofractionation (short-course treatment), given the sample size of 400 patients. Variables that may affect outcomes such as chemotherapy regimen, endocrine therapy and patient age will be assessed for impact to ensure balance between both treatment arms.

Table: Effect size and power for superiority tests		
Reconstruction Success Likelihood (%)		Power (%)
Long-course radiation	Short-course radiation	
71.0	82.8	80
71.0	84.4	90

N=400 randomized patients and α (two-sided)=0.05

[figure not shown]
Data monitoring of local/regional recurrence event:

We will also follow oncologic outcomes to exclude any unexpected increase in the risk of recurrence with hypofractionation (short-course) radiation therapy, although a detectable increase in recurrence rates is unlikely given data from prior experiences of hypofractionation. The cumulative incidence of local or regional recurrence in a recent series of post-mastectomy

radiation therapy is about 2% at 18 months.³ Therefore, in the case where the recurrence rate is suggested to be statistically significantly greater than 2%, the study will be suspended to allow for investigation.

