Local/regional recurrence event rate monitoring will occur at the first meeting of the DF/HCC Data and Safety Monitoring Board (DSMB) and continue until the last patient has completed radiation. Data analysis will be performed every 6 months (see Section 11). Specifically, the event rate and corresponding 0.95 exact binomial confidence interval will be calculated, where the numerator is the number of the local/regional recurrence events and the denominator is the number of patients who have completed short-course treatment at time of analysis. The results will be reviewed by the DSMB. If the lower boundary of the 0.95 confidence interval is greater than 2%, accrual of the study will be suspended and a decision will be made as to whether accrual can be resumed or if the study should be closed by the study team in consultation with the DSMB, IRB and study advisory board. The boundary for this criterion is shown in “**Figure: Stopping boundary for local/regional recurrence-event monitoring**”. With the sample size of 200 in the short-course radiation arm, the probability that the interim data meet the stopping criteria (see figure) in the course of the trial is 72% if the true local or regional recurrence rate were 5%. It would be 98% if the true recurrence rate is 8% at 18-months.

Figure: Stopping boundary for local/regional recurrence-event monitoring

There has been no suggestion of increased rare radiation side-effects or mortality with hypofractionation (short-course) radiation therapy with long term follow up in the studies using hypofractionation.^{23,24,31} Therefore, we do not expect any increased risk of side-effects in our short-course arm. Nevertheless, to be extra cautious, we will follow these outcomes in our patients. We recognize that our study is too short to detect differences in long-term distant recurrence, cardiac mortality and overall mortality. Therefore, we will create an infrastructure with which monitor these outcomes and apply for additional funding for longer follow up.

10e. Heterogeneity in treatment (HTE) outcomes

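### Objective 2 hypothesises no increase in side-effects, but Section 10f plans only Fisher's exact test of a difference, which cannot support that hypothesis and has little power for rare toxicities

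*Combined protocol and SAP*

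**What the plan says.** Section 2.2, Objective 2, hypothesises that short-course therapy "will have no increased risk of local or regional recurrence or side-effects". Under the same objective the protocol undertakes to monitor "rare radiation side effects (secondary malignancy and brachial plexopathy" over the long term. The recurrence-monitoring text in Section 10 repeats the expectation: "we do not expect any increased risk of side-effects in our short-course arm".

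Section 10f describes the analysis. Event rates are tabulated per arm by seriousness, grade and attribution. On inference, the section says only that "they will be compared between the arms by using Fisher’s exact test". The DSMB reviews toxicity every six months. Section 10f states no significance level, analysis population, interval, margin, expected rate or power.

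Other Objective 2 outcomes are treated differently. Section 10c plans a two-sided 95% confidence interval for the difference in reconstruction success. Recurrence in the short-course arm is monitored with an exact 95% interval.

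**The concern.** The hypothesis and the analysis do not match. The hypothesis is that there is no excess, whereas Fisher's test takes equality as its null. A small p-value would count against the hypothesis. A large one leaves it unresolved, because it arises both when the risks are equal and when there are too few events to tell. Without an interval or a stated excess to exclude, the planned output cannot separate the two.

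This matters here because Section 1.1 acknowledges that data on hypofractionation after mastectomy and with nodal irradiation are limited, and says that high-quality randomised evidence is needed to change practice. Readers will look to this trial for toxicity after reconstruction. A p-value alone would not tell them how large an excess remains possible.

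**Working it through.** **Inputs from the documents.** Section 5.3: "400 patients will be randomized 1:1 into either Arm 1 (short-course PMRT) or Arm 2 (long-course PMRT"), so 200 per arm. Section 10c, for the reconstruction-success test: "N=400 randomized patients and α (two-sided)=0.05". Section 10f does not state a level for Fisher's test, so two-sided 0.05 is assumed.

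**Input not in the documents.** No adverse event rate is given. Control risks from 1% to 10% are assumed for illustration. Section 1.1 describes brachial plexopathy as extremely rare and pneumonitis as much less likely than lymphedema, but attaches no figures.

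**Step 1: check of sample size and level.** The plan states no power for adverse events. Its nearest figures are 80% and 90% for reconstruction success of 71.0% against 82.8% and 84.4%. With p̄ the mean of the two proportions, the chi-square approximation is

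power = Φ{[|p₂ − p₁| − 1.96·√(2p̄(1 − p̄)/200)] / √([p₁(1 − p₁) + p₂(1 − p₂)]/200)}.

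This gives Φ(0.848) = 80.2% and Φ(1.276) = 89.9%. Both reproduce the plan.

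**Step 2: power of Fisher's test for a doubling.** Let X be the number of events on long-course, Binomial(200, p), and Y the number on short-course, Binomial(200, 2p). Exact power is the sum of P(X = x)·P(Y = y) over all pairs (x, y) whose two-sided Fisher p-value is at most 0.05.

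| Long-course risk | Short-course risk | Power | Chance of non-significance |
|---|---|---|---|
| 1% | 2% | 4% | 96% |
| 2% | 4% | 13% | 87% |
| 3% | 6% | 23% | 77% |
| 5% | 10% | 41% | 59% |
| 6% | 12% | 49% | 51% |
| 10% | 20% | 77% | 23% |

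Power passes 50% just above a 6% control risk (53% at 6.5%). With 190 per arm (applying the 5% dropout that Section 10b expects at 6 months) it is 4%, 12%, 38% and 75% at 1%, 2%, 5% and 10%.

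**Step 3: what an interval would show.** For each arm take the Wilson score limits l and u around the observed p. The Newcombe 95% limits for the difference d = p_S − p_L are

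lower = d − √[(p_S − l_S)² + (u_L − p_L)²], upper = d + √[(u_S − p_S)² + (p_L − l_L)²].

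At equal observed counts:

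| Events per arm | Observed rate | Wilson limits | Half-width of the difference |
|---|---|---|---|
| 2/200 | 1% | 0.27% to 3.57% | 2.7 points |
| 4/200 | 2% | 0.78% to 5.03% | 3.3 points |
| 10/200 | 5% | 2.74% to 8.96% | 4.6 points |

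For 4/200 in each arm: √[(2.00 − 0.78)² + (5.03 − 2.00)²] = √(1.49 + 9.18) = 3.3 points. Fisher's p is 1.0, yet an excess of up to 3.3 points remains compatible with the data. A doubling from 2% is an excess of 2 points, so it is not excluded. At 1% a doubling (1 point) is not excluded either. At 5% it (5 points) just is, with a limit of 4.6.

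At 4/200 on long-course against 8/200 on short-course, p = 0.38 and the difference is 2.0 points (−1.6 to 5.9). At 10/200 against 20/200, p = 0.086 and the difference is 5.0 points (−0.2 to 10.4). In both cases the p-value is non-significant and the interval admits a substantial excess.

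**The case against.** The strongest reply is that Section 10f is headed as monitoring. The plan's confirmatory weight rests on the FACT-B physical well-being score and, for Objective 2, on reconstruction success. A reader might infer that a non-significant Fisher test is meant to be reported as showing safety. The documents do not support this: no section states a rule for concluding safety, and the monitoring text says only that these outcomes will be followed as a precaution. What stands against the plan is narrower. Objective 2 does state the hypothesis, and no other planned inference on side-effects addresses it.

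Second, low power is not general. Section 10f covers all event types and grades, and at a 10% control risk a doubling is detected 77% of the time. That is correct, so the power argument is confined to control risks below about 6%. The mismatch between hypothesis and test does not depend on the rate.

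Third, other safeguards exist: per-arm rates, DSMB review, the recurrence rule, and the interval for the reconstruction composite, which includes major complications. These are real, but none gives a between-arm difference in a named side-effect with its uncertainty. Section 10 also concedes that the study is too short for differences in long-term distant recurrence, cardiac mortality and overall mortality. It does not extend that caveat to side-effects.

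Fourth, Section 6.6 lets women move from short- to long-course when dose-homogeneity limits cannot be met. A reader might infer that analysis as randomised materially hides an excess. Dilution is possible in principle, but no switching rate is given and its size cannot be stated. Comparing women by treatment received is no cure, because those who switch are selected on planning difficulty.

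**Conclusion.** The point holds. Objective 2 claims "no increased risk of local or regional recurrence or side-effects", and for side-effects the plan supplies only a test of equality, with no risk difference, interval, margin or power. Such a test cannot support the claim. For control risks below about 6%, the likely range for events the protocol itself calls rare, it has under 50% power to detect a doubling: 4% at 1%, 13% at 2% and 41% at 5%. The power figures assume 200 evaluable women per arm, two-sided 0.05 and the illustrative rates shown.

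The documents do not establish that safety will be declared from a non-significant result, or that low power applies to common toxicities. The defect is worth correcting because an informative analysis of the same data is available at almost no cost and the plan already uses an interval for reconstruction success. The primary endpoint is unaffected.

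**What to change.** In Section 10f, for each event type listed as reportable in Section 7.2:

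- Report the short-minus-long risk difference, as randomised, with a 95% score (for example Newcombe) or exact confidence interval, and state the largest excess that the data exclude. A simple Wald interval should be avoided at these counts: at equal rates of 1%, 2% and 5% its half-width, 1.96·√(2p(1 − p)/200), is 2.0, 2.7 and 4.3 points, against 2.7, 3.3 and 4.6 by Newcombe.
- Keep Fisher's p-value as descriptive, and state that non-significance will not be taken as evidence of no increase.
- If wanted, add a table by treatment received as a sensitivity analysis only, noting that it is not protected by randomisation.

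The cost is SAP wording and an extra table column, with no new data collection. The downside is that the report will have to show openly that moderate excesses in rare toxicities are not excluded.
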